#### 1. Limitations with mobility or walking

Examples might include ankle turning, not being able to walk to the front door fast enough when there is a caller, needing help to move around the home. You can choose a different example.

The sign or symptom causing concern is:

How severe is the sign or symptom? Place a vertical mark on the line below to indicate how bad you think the sign or symptom has been over the past week, including today.

[figure not shown]

#### 2. Problems with hands or arms

Examples might include not being able to do up buttons, or type at a computer keyboard. You can choose a different example.

The sign or symptom causing concern is:

How severe is the sign or symptom? Place a vertical mark on the line below to indicate how bad you think the sign or symptom has been over the past week, including today.

[figure not shown]

#### 3. Inability to do activities

Examples might include not being able to visit family, do cleaning in the home, take a bath or shower. You can choose a different example.

The sign or symptom causing concern is:

How severe is the sign or symptom? Place a vertical mark on the line below to indicate how bad you think the sign or symptom has been over the past week, including today.

Study AMO-02-MD-2-001	Site no.  /  / 	
	Subject no.  /  / 	

### Clinician Domain-Specific Causes for Concern: Myotonic Dystrophy - Page 2 of 5

Please rate the causes for concern associated with the subject's myotonic dystrophy that you would most like to see change during treatment in the categories below. You can select any sign or symptom fitting the category.

#### 4. Fatigue

Examples include lacking the energy to perform work activities, or finding walking too exhausting. You can choose a different example.

The sign or symptom causing concern is:

How severe is the sign or symptom? Place a vertical mark on the line below to indicate how bad you think the sign or symptom has been over the past week, including today.

#### 5. Pain

Examples include pain in the hands or feet. You can choose a different example.

The sign or symptom causing concern is:

How severe is the sign or symptom? Place a vertical mark on the line below to indicate how bad you think the sign or symptom has been over the past week, including today.

[figure not shown]

#### 6. Gastrointestinal issues

Examples include fecal incontinence or dyspepsia. You can choose a different example.

The sign or symptom causing concern is:

How severe is the sign or symptom? Place a vertical mark on the line below to indicate how bad you think the sign or symptom has been over the past week, including today.

#### 7. Problems with vision

Examples include blurred vision, ptosis, or ocular myotonia. You can choose a different example.

The sign or symptom causing concern is:

How severe is the sign or symptom? Place a vertical mark on the line below to indicate how bad you think the sign or symptom has been over the past week, including today.

Study AMO-02-MD-2-001	Site no.  /  / 	
	Subject no.  /  / 	

### Clinician Domain-Specific Causes for Concern: Myotonic Dystrophy - Page 3 of 5

Please rate the causes for concern associated with the subject's myotonic dystrophy that you would most like to see change during treatment in the categories below. You can select any sign or symptom fitting the category.

#### 8. Communication difficulties

An example would be difficulties with production of speech. You can choose a different example.  
The sign or symptom causing concern is:

How severe is the sign or symptom? Place a vertical mark on the line below to indicate how bad you think the sign or symptom has been over the past week, including today.

#### 9. Impaired sleep or daytime sleepiness

Examples include insomnia, or falling asleep after lunch. You can choose a different example.  
The sign or symptom causing concern is:

How severe is the sign or symptom? Place a vertical mark on the line below to indicate how bad you think the sign or symptom has been over the past week, including today.

#### 10. Emotional issues

Examples include feeling depressed or anxious. You can choose a different example.  
The sign or symptom causing concern is:

[figure not shown]
How severe is the sign or symptom? Place a vertical mark on the line below to indicate how bad you think the sign or symptom has been over the past week, including today.

#### 11. Difficulty thinking

Examples include difficulties in concentrating for long enough to complete tasks, or remembering important information. You can choose a different example.  
The sign or symptom causing concern is:

How severe is the sign or symptom? Place a vertical mark on the line below to indicate how bad you think the sign or symptom has been over the past week, including today.

Study AMO-02-MD-2-001	Site no. 	
	Subject no. 	

### Clinician Domain-Specific Causes for Concern: Myotonic Dystrophy - Page 4 of 5

Please rate the causes for concern associated with the subject's myotonic dystrophy that you would most like to see change during treatment in the categories below. You can select any sign or symptom fitting the category.

[figure not shown]
#### 12. Decreased satisfaction in social situations

Examples include not enjoying the attention of others, or not being able to participate in social activities.

You can choose a different example.

The sign or symptom causing concern is:

How severe is the sign or symptom? Place a vertical mark on the line below to indicate how bad you think the sign or symptom has been over the past week, including today.

[figure not shown]
#### 13. Decreased performance in social situations

Examples include feeling self-conscious of speaking in public, or not being able to follow group dialogues.

You can choose a different example.

The sign or symptom causing concern is:

How severe is the sign or symptom? Place a vertical mark on the line below to indicate how bad you think the sign or symptom has been over the past week, including today.

[figure not shown]

#### 14. Myotonia

Examples include myotonia in the hands or ocular myotonia. You can choose a different example.

The sign or symptom causing concern is:

How severe is the sign or symptom? Place a vertical mark on the line below to indicate how bad you think the sign or symptom has been over the past week, including today.

[figure not shown]

#### 15. Breathing difficulties

Examples breathlessness whilst walking, or sleep apnea. You can choose a different example.

The sign or symptom causing concern is:

How severe is the sign or symptom? Place a vertical mark on the line below to indicate how bad you think the sign or symptom has been over the past week, including today.

Study AMO-02-MD-2-001	Site no. 	
	Subject no. 	

### Clinician Domain-Specific Causes for Concern: Myotonic Dystrophy - Page 5 of 5

Please rate the causes for concern associated with the subject's myotonic dystrophy that you would most like to see change during treatment in the categories below. You can select any sign or symptom fitting the category.

#### 16. Choking or swallowing issues

An example would be not being able to eat easily. You can choose a different example.

The sign or symptom causing concern is:

How severe is the sign or symptom? Place a vertical mark on the line below to indicate how bad you think the sign or symptom has been over the past week, including today.

#### 17. Hearing difficulties

Examples include hearing loss or inability to follow conversations in a group situation. You can choose a different example.

The sign or symptom causing concern is:

How severe is the sign or symptom? Place a vertical mark on the line below to indicate how bad you think the sign or symptom has been over the past week, including today.

Evaluator name

Evaluator signature

Date

dd  mmmm  yyyy

17.7

**Appendix G: OSU Autism Rating Scale—DSM-IV (OARS-4)**

## **OSU Autism Rating Scale—DSM-IV (OARS-4)**

1000

A thick black horizontal bar is positioned at the bottom of the page, spanning most of the width of the content area. It serves as a visual separator or footer element.

A series of ten horizontal black bars of varying lengths, decreasing in length from left to right. The bars are evenly spaced and extend across the width of the frame.

A thick black horizontal bar with a thin white horizontal line running through its center.

1000

Page 10 of 10

\_\_\_\_\_

[REDACTED]

References:

The OSU Research Unit on Pediatric Psychopharmacology (2005, November): OSU Autism Rating Scale—DSM-IV (OARS-4). Columbus, OH: Author.

© by OSU Research Unit on Pediatric Psychopharmacology, 2005 ; investigators and clinicians may make free copies.

AUC_{0-12hr}	Area Under the Serum Concentration Time Curve from Time Zero to Hour 12
AST	Aspartate amino transferase
BMI	Body Mass Index
BP	Blood Pressure
CGI	Clinical Global Impression
CGI-I	Clinical Global Impression - Improvement scale
CGI-S	Clinical Global Impression - Severity scale
CI	Confidence Interval
C_{max}	Maximum Serum Concentration
C_{min}	Minimum Serum Concentration
C_{ss}	Steady State Concentration
DSMC	Data Safety Monitoring Committee
DRM	Data Review Meeting
DXA	Dual-energy X-ray Absorptiometry
ECG	Electrocardiography
FAS	Full Analysis Set
FVC	Forced Vital Capacity
INR	International Normalised Ratio
LLOQ	Lower Limit of Quantification
LS	Least Squares
MAR	Missing at Random
MCAR	Missing Completely at Random
MedDRA	Medical Dictionary for Regulatory Activities
MMRM	Mixed-Effect Model Repeated Measures
NHPT	Nine Hole Peg Test
NTEAE	Non-Treatment Emergent Adverse Event

OSU	Ohio State University
PK	Pharmacokinetic
PKAS	Pharmacokinetic Analysis Set
PT	Preferred Term
SAF	Safety Analysis Set
SAP	Statistical Analysis Plan
SD	Standard Deviation
SE	Standard Error
SOC	System Organ Class
T _{1/2}	Terminal Elimination Half-Life
TEAE	Treatment Emergent Adverse Event
T _{max}	Time of the Maximum Observed Serum Concentration
ULN	Upper Limit of Normal
VAS	Visual Analogue Scale
WHO	World Health Organization

1 INTRODUCTION

This document details the statistical analysis of the data that will be performed for the AMO Pharma Ltd study: A Single-Blind, Phase 2 Study to Evaluate the Safety and Efficacy of Tideglusib 400mg or 1000mg for the Treatment of Adolescent and Adult Congenital and Juvenile-Onset Myotonic Dystrophy.

The proposed analysis is based on the contents of protocol version 4.0 (dated 09-JAN-2017). In the event of future amendments to the protocol, this statistical analysis plan (SAP) may be modified to account for changes relevant to the statistical analysis.

The table, listing and figure shells are supplied in a separate document.

The analysis and statistics reporting will be conducted at [REDACTED] using SAS version 9.2 or higher.

Summary statistics will consist of number of subjects(n), mean, standard deviation (SD), minimum, median and maximum, unless specified otherwise. The precision of these variables is defined in the table, figure and listing shells document.

For categorical variables, the number and percentage of subjects in each category will be presented, based on the number of non-missing observations apart from disposition of subjects, protocol deviations, background and demographic characteristics, prior and concomitant medications and adverse events where the percentage will be based on the number of subjects in the analysis set.

Where mentioned in this SAP, "active treatment" will relate to tideglusib treatment.

Unless otherwise stated, baseline is defined as the last non-missing value (including scheduled and unscheduled assessments) prior to the subject receiving active treatment.

In the final analysis of the combined Cohort 1 and Cohort 2 subject data, data will be summarised in tabular form by the intended dose group according to the cohort (Tideglusib 400mg and Tideglusib 1000mg) apart from disposition of subjects, protocol deviations, and background and demographic data which will be summarised by dose group and overall subjects. In the analysis to be conducted at completion of Cohort 1, the data will be summarised in tabular form for the Tideglusib 1000mg dose group only.

Listings will be sorted by dose group, subject number and time of assessment.

2 STUDY OBJECTIVES AND DESIGN

2.1 Study Objectives

Primary Objective:

To investigate the safety and tolerability, between baseline and end-of-treatment, of tideglusib in adolescent and adult subjects with congenital or juvenile-onset myotonic dystrophy.

Secondary Objectives:

To investigate the blood pharmacokinetics of tideglusib in adolescent and adult subjects with congenital or juvenile-onset myotonic dystrophy.

To investigate differences in outcomes reflective of efficacy, between baseline and end-of-treatment, with tideglusib in adolescent and adult subjects with congenital or juvenile-onset myotonic dystrophy.

2.2 Study Design

This is a single-blind, [REDACTED] study in adolescent and adult subjects with congenital or juvenile-onset type 1 myotonic dystrophy.

Approximately 16 subjects in total are planned to be enrolled and receive active treatment.

Participation for individual subjects will consist of an initial Screening of up to [REDACTED] (minimum of [REDACTED]) followed by a [REDACTED] treatment phase. After this, subjects in Cohort 1 will be treated with single-blinded 1000mg tideglusib once daily orally for 12 weeks and Cohort 2 will be treated with single-blinded 400mg tideglusib once daily orally for 12 weeks. A follow up visit will take place approximately [REDACTED] after the end of treatment visit.

Once [REDACTED] out of the [REDACTED] subjects from Cohort 1, who have received active treatment with [REDACTED] of tideglusib, have completed active treatment or discontinued from the study [REDACTED] the Data Safety Monitoring Committee (DSMC) will meet to review the available data and a recommendation will be made to the Sponsor whether Cohort 2 should be initiated. [REDACTED]

Active dosing of Cohort 2 will only start when the [REDACTED] tideglusib. No screening will take place for Cohort 2 until after the recommendation has been made from the DSMC, to the Sponsor, on if Cohort 2 should be initiated.

If the decision is made to enrol all Cohort 2 subjects on the [REDACTED] dose then the summaries and analyses described in this SAP will be updated to analyse all subjects from cohorts 1 and 2 as a single dose group in the final analysis at the end of the study.

All outputs specified in this SAP will be produced for the final analysis of the combined Cohort 1 and Cohort 2 subject data. The exceptions to this are the by subject line plots detailed within Sections 5.1.1, 5.1.2, 5.1.3 and 5.1.4.1, as well as the ad hoc Cohort 1 outputs specified in section 3.1. These specific outputs will only be produced for the Cohort 1 analysis (see Sections 3 and 3.1) and will be included in the final study report as a separate set of Cohort 1 specific analyses on this data cut. They will not be reproduced on subsequent data unless, at the end of the study, it is considered beneficial to produce these again as part of ad hoc analyses.

See protocol section 8.3 for full detail of the study design.

2.3 Visit Structure

The visit structure and scheduled assessments are detailed in Table 1: Schedule of Events in the study protocol. Throughout this SAP, visits have been referred to either according to visit number or to the corresponding week number. The table below

indicates the relationship between visit number and week number. Visits will be referred to by week number in the tables, figures and listings, as described in Section 1 of the table, figure and listing shells.

Table 1: Visit labels

Visit	1	2	3	4	5	6	7	8	9
Week	1	2	3	4	5	6	7	8	9

2.4 Sample Size

Sufficient subjects will be entered into the study to ensure at least 16 are dosed with tideglusib. Enrolment will occur at one, or maybe two, study sites. Eight subjects will be dosed in each of the two dose groups.

No formal sample size calculation was performed.

2.5 Changes from the Protocol Planned Analysis

There is no planned analysis of the protocol defined secondary endpoints relating to the biomarker [REDACTED]

There are no further changes to the protocol planned analyses.

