### 8.2 Secondary endpoints

Secondary endpoints will include the following:

- Blood pharmacokinetics (PK) of tideglusib
- 10 metre walk/run test (self-selected and fastest velocity)
- Computerised handgrip myometer measure of grip strength and muscle relaxation time
- Respiratory Forced vital capacity (FVC)
- Clinical Global Impressions– Severity and –Improvement (CGI-S and CGI-I)
- Actigraphy (measure daily averages of: number of bouts of activity, number of steps taken and energy expenditure)
- Nine Hole Peg Test (NHPT)
- Dual-energy X-ray absorptiometry (DXA) whole body scan of lean muscle mass (g) legs, arms, and total
- Top 3 Concerns VAS (caregiver-completed and where possible, subject-completed also)
- OSU Autism Rating Scale (OARS)
- OSU Autism CGI
- Clinician-completed Domain Specific Cause for Concern VAS: Myotonic Dystrophy
- Peabody Picture Vocabulary Test
- [REDACTED] levels and activity

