#### **10.2.4 Actigraphy**

Actigraphy is a non-invasive method of monitoring physical activity via an actigraph device. The Actigraph device will be worn on the waist during waking hours, according to the device's instruction manual.

In this study, actigraphic assessments will occur on a regular basis throughout the study as detailed in the schedule of assessments. Each assessment will consist of approximately 7 full days of activity information from subjects, and this information will be used to calculate the average number of steps per day, bouts of activity and total energy expenditure.

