### 11.2 Study Populations

Assignment of subjects to analysis populations will be agreed prior to database lock.

The Safety Set (SAF) will include all subjects who took at least one dose of tideglusib. The SAF will be used for all summaries of safety data.

The Full Analysis Set (FAS) will include all subjects in the SAF for whom any efficacy data were collected after first dose of tideglusib. The FAS is the primary population for analyses of efficacy data.

The Per Protocol Set (PPS) will include all subjects in the FAS who did not have any major protocol violations. Definitions of major and minor protocol violations will be included in the SAP. If no subjects are excluded from the PPS, the PPS will not be required. The PPS will be used for secondary analyses of efficacy data.

The Pharmacokinetic Analysis Set (PKAS) will consist of all subjects for whom Pharmacokinetic samples were taken for the derivation of Pharmacokinetic parameters and for whom the corresponding time since last dose prior to sampling is available.

Listings of study data will be based on all subjects who were enrolled in the study.

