4 STUDY SUBJECTS

4.1 Disposition of Subjects

The number and percentage of all subjects enrolled, included in the full analysis set, safety analysis set, pharmacokinetic analysis set, who completed the study, prematurely discontinued treatment (where the subject discontinued prior to []), prematurely discontinued the study and study duration (date of completion/discontinuation – Visit [] date + 1) will be summarised. The number and percentage of subjects will be summarised by their reasons for withdrawal from treatment (i.e. prior to [] and separately from the study (i.e. prior to [])). Eligibility for each of the analysis sets along with reasons for exclusion will be listed. Study completion/withdrawal data will be listed.

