4.1.1 Analysis Sets

The **Enrolled Set** includes all subjects who passed screening irrespective of whether they received active treatment. The enrolled set will be used for subject disposition summaries.

The **Safety Analysis Set (SAF)** will include all subjects who had at least one administration of active treatment. The SAF will be used for all summaries of protocol

deviations, background and demographic characteristics, administration of investigational product and safety evaluation data.

The **Full Analysis Set** (FAS) will include all subjects in the SAF for whom any efficacy data were collected after first administration of active treatment. The FAS is the primary population for analyses of efficacy data.

The **Pharmacokinetic Analysis Set** (PKAS) will consist of all subjects for whom PK plasma concentration data (which includes concentrations below the lower limit of quantification (LLOQ)) are available at either [REDACTED] or [REDACTED] (pre-dose or post-dose).

Listings of study data will be based on all subjects who were enrolled in the study.

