5.1.1.4 Actigraphy

For each subject and visit, actigraphy data will be selected for analysis based on the following rules:

1. Take the first 7 consecutive days following the visit date (where Day 1 of the 7 days is the day after the visit date).
2. Exclude the first and last of these 7 days to leave 5 consecutive days.
3. Considering the remaining 5 days, exclude any day with less than 5 hours of wear time in total (this does not have to be consecutive hours).
4. Following the above steps, if less than 3 days remain, exclude all actigraphy data for this visit for the subject (visit is treated as missing and subject to the imputation methods outlined in this SAP for MMRM analyses)

Following application of the above rules, an assessment will be performed to determine how many subjects have non-missing data meeting the criteria at each of the visits (with particular reference to Baseline and [REDACTED] [REDACTED])

For each subject and visit, the measurements to be summarised and analysed will be 'Weekly total per hour of wear time'. This will be derived as the total value across all valid days for the visit (selected in steps 1-4 above) divided by the total hours wear time across these valid days. This calculation will be performed separately for

the weekly total number of steps per hour of wear time, weekly total number of 3 minute bouts of activity per hour of wear time, weekly total number of >10 minute bouts of activity per hour of wear time. A 3 minute bout of activity will consist of 3 minutes of activity, with zero minutes 'drop time' and 300 activity counts per minute.

The weekly total number of steps per hour wear time, total number of 3 minute bouts of activity per hour wear time, total number of >10 minute bouts of activity per hour wear time will be derived at each visit from [redacted] onwards.

Baseline will be taken from the 7 days of activity recorded commencing from the day after the [redacted] date. The Actigraph activity recorded during the 7 days following each visit, will be assigned to the next visit i.e. the actigraphy data recorded during the 7 days commencing the day after the [redacted] (week [redacted]) date will be assigned to [redacted] (week [redacted]) and so on.

A MMRM model will be fitted to the change from baseline to the above assigned weeks [redacted] in the weekly total number of 3 minute bouts of activity per hour wear time. The model will be fitted and results presented as described in section 5.1.1.2.

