The observed weekly total: number of steps per hour wear time, number of 3 minute bouts of activity per hour wear time and number of >10 minute bouts of activity per hour wear time and the corresponding change from baseline will be summarised. The weekly totals per hour wear time will also be presented using by subject line plots over time (assigned [redacted] (baseline), assigned [redacted], assigned [redacted] and assigned [redacted] by dose group. In addition, line plots will present the adjusted LS mean changes from baseline and SEs over time, as estimated by the MMRM model, by dose group for the weekly total number of 3 minute bouts of activity per hour wear time.

Actigraphy data will be listed.

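### SAP 2.5 states that nothing else has changed, yet energy expenditure, the Per Protocol Set and the conditional site effect are dropped without being declared

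*SAP*

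**What the plan says.** SAP 2.5 names one departure, the biomarker, and closes with "There are no further changes to the protocol planned analyses".

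**Energy expenditure.** Protocol 8.2 lists actigraphy as a secondary endpoint with "daily averages of: number of bouts of activity, number of steps taken and energy expenditure". Protocol 10.2.4 says the recordings will be used to "calculate the average number of steps per day, bouts of activity and total energy expenditure". SAP 5.1.1.4 derives steps, 3 minute bouts and bouts above 10 minutes. Its summary sentence starts "The observed weekly total: number of steps per hour wear time, number of 3 minute bouts of activity per hour wear time" and ends with the longer bouts. Energy expenditure is not mentioned.

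**Per Protocol Set (PPS).** Protocol 11.2 defines it as FAS subjects without a major violation and states "The PPS will be used for secondary analyses of efficacy data". It waives the set only when nobody is excluded. SAP 4.1 counts subjects "included in the full analysis set, safety analysis set, pharmacokinetic analysis set", with no PPS. SAP 4.1.1 defines the Enrolled Set, SAF, FAS and PKAS and says "The FAS is the primary population for analyses of efficacy data", but names no secondary population. SAP 4.2 still classes deviations as major or minor.

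**Site.** The synopsis and Protocol 11.5 put study site in the efficacy models as a fixed effect when more than one site takes part. SAP 2.4 still allows a second site. The MMRM in SAP 5.1.1.1 has baseline, dose group, visit and the dose-by-visit interaction. The ANCOVA in SAP 5.1.2.1 has baseline and dose group. Neither has site.

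**The concern.** Section 2.5 is where a reader looks to learn how the analysis departs from the protocol. Its closing sentence tells that reader not to look further, and a comparison of the two documents shows that it is wrong.

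If the SAP is followed as written, a named secondary measure is never summarised. If a subject has a major deviation, the protocol's secondary efficacy analysis has no instruction behind it. If a second site enrols, no model accounts for it.

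Timing adds to this. SAP 3.1 describes the review of the planned Cohort 1 outputs, and the ad hoc requests that followed, in the past tense. This version therefore post-dates a look at data on up to 8 of the 16 planned subjects. Because the three omissions are not declared, a reader cannot place them before or after that look.

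**Working it through.** The documents give no power or sample size calculation, so there is no planned figure to reproduce. The check is a comparison of the documents, followed by the cost of restoring what is missing.

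**1. Actigraphy measures.** The protocol names bouts, steps and energy expenditure. The SAP handles bouts (in two lengths) and steps, so 1 of 3 named measures has no analysis. Among those kept, only the 3 minute bouts are modelled. Steps and longer bouts are summarised.

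**2. Site term.** Efficacy models in the readable text of SAP 5.1:
- MMRM (12): walk at preferred speed, grip strength, relaxation time, FVC, 3 minute bouts, NHPT, CGI-I, clinician VAS, caregiver top 3, subject top 3, OSU autism rating scale, OSU CGI-I.
- ANCOVA (4): CGI-S, OSU CGI-S, PPVT, DXA total lean mass.

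12 + 4 = 16, and 0 of 16 has a site term, even a conditional one.

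**3. PPS.** None of the 16 models is planned on a PPS. Could one exclusion matter? If one of 8 subjects differs from the mean of the other seven by D, removing that subject moves the dose mean by D/8. For D of 1, 2 or 3 SD (assumed) the shift is 0.125, 0.25 or 0.375 SD. The standard error is √(1/8) = 0.3536 SD, so the shift is 0.35, 0.71 or 1.06 standard errors. This shows that an effect is possible, not how large it will be. With one subject excluded, residual df are 15 − 3 = 12 and that group's interval widens by √(8/7) × 1.0085 = 1.078, or 7.8%.

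**4. Cost of a site term.** Take the end-of-treatment ANCOVA with 8 + 8 = 16 subjects. Residual df fall from 16 − 3 = 13 to 16 − 4 = 12. The 97.5% t quantile rises from 2.1604 to 2.1788, a ratio of 1.0085. Let *a* and *b* be the numbers of second-site subjects in the 1000 mg and 400 mg groups, and S = a(8−a)/8 + b(8−b)/8. In units of residual variance, ignoring the baseline covariate apart from its df:
- dose LS mean at the observed site shares: 1/8 + ((b−a)/16)²/S, against 1/8 without site;
- dose difference: 1/4 + ((b−a)/8)²/S, against 1/4 without site.

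Interval ratio = √(variance ratio) × 1.0085. All site splits are assumptions.

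| a, b | S | LS mean variance | LS mean interval | Difference variance | Difference interval |
|---|---|---|---|---|---|
| equal | > 0 | 0.1250 | +0.9% | 0.2500 | +0.9% |
| 1, 3 | 2.75 | 0.1307 | +3.1% | 0.2727 | +5.3% |
| 0, 3 | 1.875 | 0.1438 | +8.2% | 0.3250 | +15.0% |
| 0, 4 | 2.0 | 0.1563 | +12.8% | 0.3750 | +23.5% |
| 0, 8 | 0 | not estimable | – | not estimable | – |

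The rows with a = 0 matter because Protocol 9.3 fills the cohorts in sequence, so a second site might contribute to Cohort 2 only. Weighting also matters. In the 1, 3 split, giving the two sites equal weight instead of observed shares raises the 1-of-8 group's standard error to 0.4197, an interval 19.7% wider.

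**5. Scales.** Protocol 8.2 names walking velocity and 10.2.1 gives metres per second; SAP 5.1.1.1 analyses seconds. Protocol 8.2 asks for daily averages of activity; SAP 5.1.1.4 says "the measurements to be summarised and analysed will be 'Weekly total per hour of wear time" (closing quotation mark omitted). These are not interchangeable. With assumed times of 5 s to 4 s and 20 s to 22 s, mean time worsens by (−1 + 2)/2 = 0.5 s, while mean velocity improves by (0.500 − 0.045)/2 = 0.227 m/s. With an assumed 6000 steps a day and wear falling from 12 h to 10 h, the daily average is unchanged but the hourly rate rises from 500 to 600.

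**The case against.** **The protocol defers detail to the SAP, and two of the items are conditional.** Both are true. The PPS is not needed if nobody is excluded, and site is not needed with one site. Nothing shows that either condition has occurred. But adding detail differs from removing a measure, a population and a model term while declaring no change, and the SAP neither carries the conditions forward nor says they are ruled out.

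**Redacted or separate material may cover the gap.** The score card table is blacked out, the shells are a separate document, and energy expenditure may appear in the actigraphy listing. This limits the claim to the readable text. The measure lists, set definitions and model terms are readable, however, and the redaction in 2.5 reads as the biomarker's name.

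**The scales are not hidden.** This stands. Time in seconds and activity per hour of wear are set out openly in SAP 5.1.1. The protocol's velocity wording could also be read as naming the two test conditions.

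A reader might infer that the scales were chosen after Cohort 1 data were seen. The documents do not support that. The planned Cohort 1 figures in Appendix 1 already plot the walk in seconds. Section 3 also calls for the 5.1.1 line plots, which for actigraphy are per hour of wear. Both belong to the set reviewed before the ad hoc requests.

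**Conclusion.** The no-further-changes sentence in SAP 2.5 is incorrect and should be corrected. Three items are dropped without being declared: energy expenditure outright (1 of 3 actigraphy measures), and the PPS and site effect conditionally (absent from all 16 models). The last two affect results only if someone is excluded or a second site enrols. All are secondary efficacy matters in an unpowered study whose primary endpoint is safety, so this should be fixed but does not undermine the main analysis. The two scales are a listing omission only.

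Two further inferences go beyond the documents. Selective omission after the Cohort 1 review is not shown: the timing of the three omissions is unknown, and no more can be said. Nor is the protocol's SAE window from screening a further undeclared SAP departure, because Protocol 11.4 itself confines safety summaries to subjects who took tideglusib.

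The omissions rest on the text alone. The interval figures rest on assumed site splits and ignore the baseline covariate apart from its df.

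**What to change.** - **Energy expenditure:** derive and summarise it with the valid-day rules of SAP 5.1.1.4, as for steps. A model is optional; requiring one would treat it more fully than steps.
- **PPS:** restore the definition and the disposition count. If anyone is excluded, run secondary efficacy analyses on the PPS, using the SAP 4.2 classification. The protocol does not require all 16 models to be repeated.
- **Site:** add a fixed effect if two sites enrol and both are represented in at least one dose group, with LS means at observed site shares. If site and dose are fully aliased, state that they cannot be separated.
- **Alternatively,** list each omission in 2.5 with its reason and whether it was decided before or after the Cohort 1 review.
- **Housekeeping:** list the walk in seconds and actigraphy per hour of wear in 2.5, with reasons.

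The cost is SAP wording, one added summary and conditional re-runs. The protocol already provides for collecting the data. Any loss of precision arises only if a second site enrols or the PPS is triggered, and the PPS loss falls on a secondary analysis only.
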